3.2. Sample size

Approximately 86 healthy subjects will be enrolled (72 subjects for treatment and up to 14 potential replacement subjects). Subjects will be randomized to one of 8 different active treatment arms (i.e. 8 per treatment arm) or placebo. This study did not have any formal sample size or power calculations. Doses expected to characterize the dynamic range of the primary PD parameter (LDL-C) were selected. A total of 8 subjects are planned per dose as a typical sample size for estimating values and variability of PK and PD measures in single ascending dose trials.

4. Study Endpoints

4.1. Primary Endpoints

- Peripheral blood low density lipoprotein-C (LDL-C) area under the effect curve from time zero to last on-study timepoint (AUEC_{0-t_l}, referred to as AUEC for brevity).
- Maximum decrease from baseline in LDL-C (Δ LDL-C_{min})

4.2. Secondary Endpoints

- Area under the curve (AUC) of evolocumab and alirocumab from time zero to infinity (AUC_{0-inf})
- Maximum concentration (C_{max}) of evolocumab and alirocumab
- Peripheral blood apolipoprotein B-100 (ApoB) $AUEC_{0-t}$.
- Maximum decrease from baseline in ApoB ($\Delta ApoB_{min}$)
- Model parameter estimates for evolocumab and alirocumab exposure-response models (exposure parameter versus $AUEC_{0-t}$ or $\Delta LDL-C_{min}$)

4.3. Exploratory Endpoints

- Peripheral blood proprotein convertase subtilisin/kexin type 9 (PCSK9) $AUEC_{0-t}$.
- Maximum decrease from baseline in PCSK9 ($\Delta PCSK9_{min}$)
- Additional pharmacokinetic parameters for evolocumab and alirocumab, including time of maximum concentration (T_{max}), elimination rate constant (K_{el}), area under the curve from time 0 to end of study (AUC_{0-t}), half-life ($t_{1/2}$), apparent clearance (CL/F), and apparent volume of distribution (V/F).
- Time course profiles, maximum increase/decrease from baseline, and AUEC for plasma proteomics and small RNA transcriptomics (set of markers be determined)

5. Analysis Populations

- For all analyses, subjects will be analyzed according to the dose and treatment received, not the dose and treatment to which subjects were randomized.
- Subjects who discontinued from the study before their assigned end of study day (referred to as early termination subjects) will be excluded from pharmacokinetic and pharmacodynamic parameter summary calculations.
- The PD population will include all subjects who receive study drug and have at least 1 estimable PD parameter after dosing. For baseline-adjusted analyses, subjects must also have at least one valid baseline sample between screening to dose administration on day 1. Subjects without a valid baseline sample will be excluded from PD assessments where the derived metric is baseline adjusted.

- The PK population will include all subjects who receive study drug and have at least 1 estimable PK parameter after dosing. Subjects with all samples below the lower limit of quantification will not be included in PK population summaries.
- The PK/PD population (exposure-response population) will include all subjects from the PK and PD populations, including subjects treated with placebo or subjects where all PK samples were below the lower limit of quantification. The PK/PD population will be used for the model-based exposure-response analysis.
- The safety population will include all subjects who receive at least 1 dose of any of the study drugs.

6. Data Screening and Acceptance

6.1. Handling of Missing and Incomplete Data

The following imputation of missing values will be done:

- Pharmacokinetic measurements below the quantification limits will be considered equal to zero for all analyses.
- Non-pharmacokinetic measurements (e.g., LDL-C, ApoB, PCSK9) below the quantification limits will be considered equal to the lower limit of quantification for all analyses unless explicitly noted otherwise.
- Missing pharmacokinetic or pharmacodynamic data (e.g., skipped out patient visit) will not be imputed.
- For baseline adjusted measures, samples from Day 1, time 0 will be used for calculating this derived metric. In cases where the Day 1, time 0 sample is missing or invalid, the sample collected at check-in (Day -1) will be used, followed by the screening sample. If none of these samples are available or valid, then no baseline value will be calculated for the subject.

7. General Statistical Considerations

All data will be presented in data listings. Data from subjects excluded from the analysis population will be presented in the data listings, but not included in the calculation of summary statistics.

7.1. Subject Disposition

The number of subjects who enroll in the study and the number and percentage of subjects who complete each assessment will be presented. The frequency and percentage of subjects who withdraw or discontinue from the study and the reason for withdrawal or discontinuation will be summarized. In addition, significant known protocol deviations will be noted for individual subjects.

7.2. Demographics and Baseline Characteristics

Descriptive statistics will be used to summarize demographic and baseline subject characteristics for age, sex, weight, body mass index, race, and ethnicity. For continuous variables, the mean, median, standard deviation (SD), minimum, and maximum values will be reported. For categorical (nominal) variables, the number and percentage of subjects (or observations) will be reported.

7.3. Pharmacodynamic Analysis

7.3.1 LDL-C

Individual LDL-C versus time plots will be presented for each participant. For LDL-C, AUEC and maximum decrease from baseline will be calculated for each participant using all on treatment timepoints. Calculations will be performed using non-compartmental analysis packages available in statistical software. The primary analysis with LDL-C will use baseline adjusted AUEC and maximum decrease from baseline; other derived AUEC measures may be calculated (AUEC calculation without baseline adjustment and with normalization to baseline [pAUEC]) to evaluate how derived PD metrics impact trial design. PD parameters of evolocumab, alirocumab, and placebo groups will be listed and summarized using descriptive statistics (n, mean, SD, coefficient of variation, minimum, median, interquartile range, and maximum) for each treatment arm.

7.3.2 ApoB and PCSK9

Individual ApoB and PCSK9 versus time plots will be presented for each participant. For ApoB and PCSK9, baseline-adjusted AUEC and maximum decrease from baseline will be calculated for each participant using all on treatment timepoints. Calculations will be performed using non-compartmental analysis packages available in statistical software. The secondary analysis with ApoB will use baseline adjusted AUEC and maximum decrease from baseline. The exploratory analysis with PCSK9 will use baseline adjusted AUEC and maximum decrease from baseline. Other derived AUEC measures for ApoB and PCSK9 may be calculated (AUEC calculation without baseline adjustment and with normalization to

baseline [pAUEC]) to evaluate how derived PD metrics impact trial design. PD parameters of evolocumab, alirocumab, and placebo groups will be listed and summarized using descriptive statistics (n, mean, SD, coefficient of variation, minimum, median, interquartile range, and maximum) for each treatment arm.

7.4. Pharmacokinetic Analysis – Alirocumab and Evolocumab

Individual serum concentration versus time plots for evolocumab and alirocumab groups will be presented for each participant. AUC_{0-inf} and C_{max} will be calculated for each participant using all on treatment timepoints as part of the secondary analysis. In addition, the following PK parameters will be calculated for each individual as exploratory analyses: AUC_{0-t} , T_{max} , apparent clearance (CL/F), apparent volume of distribution (V/F), elimination rate (Kel), and terminal half-life ($t_{1/2}$). PK parameters will be calculated for each participant using all on treatment timepoints. All parameters will be summarized using descriptive statistics (n, geometric mean, coefficient of variation, minimum, median, interquartile range, and maximum) for each alirocumab and evolocumab treatment arm.

Calculations will be performed using non-compartmental analysis packages available in statistical software. Serum concentrations below the limits of quantification will be set to zero for the purpose of this analysis. Subjects with all samples below the limit of quantification will be excluded from PK summaries. AUC_{0-inf} , $t_{1/2}$, and Kel for subjects will only be included for subjects with 3 or more concentration values on the terminal portion of the pharmacokinetic curve and with an adjusted coefficient of determinations (R^2) greater than 0.80.

7.5. PK/PD Analyses

The dose- and exposure-response relationship between baseline-adjusted AUEC for LDL-C and $\Delta LDL-C_{min}$ and alirocumab and evolocumab will be explored graphically (separate assessments for both response measures). Based on these observations, model-based analyses using statistical software will be conducted separately for each drug with respect to each of the above-mentioned PD measures.

The model-based analysis will explore both dose and exposure (i.e., AUC_{0-inf} , referred to as AUC below) as the dependent variable. All dose levels for a drug, as well as placebo data, will be

combined for the analysis. Model selection will be based on the initial graphical assessment and will be selected from one of the following structures – linear, E_{\max} , and sigmoidal. Multiple models may be evaluated based on the initial graphical analysis, in which case model selection will be based on a combination of goodness of fit plots, parameter uncertainty (i.e., parameter confidence intervals including zero), and Akaike’s information criterion (AIC). General representations for each of the model structures and parameterizations is shown below:

Dose-relationship

Linear: Response $\sim E_0 + \text{Slope} * \text{Dose}$

E_{\max} : Response $\sim E_0 + E_{\max, \text{dose}} * \text{Dose} / (\text{Dose} + ED_{50})$

Sigmoidal: Response $\sim E_0 + E_{\max, \text{dose}} * \text{Dose}^\gamma / (\text{Dose}^\gamma + ED_{50}^\gamma)$

Exposure-relationship

Linear: Response $\sim E_0 + \text{Slope} * \text{AUC}$

E_{\max} : Response $\sim E_0 + E_{\max, \text{exp}} * \text{AUC} / (\text{AUC} + EC_{50})$

Sigmoidal: Response $\sim E_0 + E_{\max, \text{exp}} * \text{AUC}^\gamma / (\text{AUC}^\gamma + EC_{50}^\gamma)$

Model evaluation will include residual variability error term but will not include any random effects or covariate evaluation on fixed effect.

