3.1. Study Design

This is a randomized, double-blind, placebo-controlled, single-dose, parallel arm, pilot study. Healthy subjects will be randomized to one of four dose groups (low, intermediate low, intermediate high, and high) for each drug (evolocumab or alirocumab) or placebo (See Table 1). The study will be conducted at one center in the United States (Spaulding Clinical Research unit in West Bend, Wisconsin).

All subjects will be sampled daily for the first week. Subjects in groups A, B, E, and F will follow the schedule of events through day 42. Subjects in groups C and G will follow the schedule of events through day 56. Subjects in groups D, H, and I will follow the schedule of events through day 84. Each treatment group should include equal representation of male and female subjects.

Table 1: Study Treatment Groups

Subjects (n)	Treatment Group	Drug
8	A	Evolocumab low (21 mg) subcutaneously (SC)
8	B	Evolocumab intermediate low (35 mg) SC
8	C	Evolocumab intermediate high (70 mg) SC
8	D	Evolocumab high (140 mg) SC
8	E	Alirocumab low (15 mg) SC
8	F	Alirocumab intermediate low (25 mg) SC
8	G	Alirocumab intermediate high (50 mg) SC
8	H	Alirocumab high (100 mg) SC
8	I	Placebo SC

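### SAP 7.5 sets no variance structure for the AUEC models, although AUEC spread roughly doubles between the 42-day and 84-day arms; under a constant-variance fit, high-dose intervals are too narrow

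*SAP*

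**What the plan says.** SAP 4.1 defines the LDL-C AUEC as the "area under the effect curve from time zero to last on-study timepoint". SAP 3.1 makes that timepoint depend on the arm. For the two lowest doses of each drug it reads: "Subjects in groups A, B, E, and F will follow the schedule of events through day 42". The intermediate high arms (C, G) stop at Day 56, and the high-dose arms (D, H) and placebo (I) continue to Day 84.

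SAP 6.1 takes baseline from one sample, Day 1 time 0, with check-in and then screening only as fallbacks. SAP 7.3.1 adds: "The primary analysis with LDL-C will use baseline adjusted AUEC and maximum decrease from baseline".

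SAP 7.5 then puts the four doses of a drug and the placebo arm into one fit, separately for each drug, using a linear, Emax or sigmoidal model. On error it says: "Model evaluation will include residual variability error term". The same sentence rules out random effects and covariates. Models are chosen from goodness-of-fit plots, AIC, and whether parameter confidence intervals include zero. The form of the residual variance is not stated, and neither is the confidence level.

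The protocol handles AUEC noise differently. Section 5.7.2.3.1 stops the AUEC once the subject has returned to baseline, and 5.9.6.1 uses dose-specific intervals to limit noise from baseline fluctuation. The SAP has no return-to-baseline cut.

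**The concern.** An AUEC is a sum over time. A longer window accumulates more visit noise and multiplies any error in the single baseline reading by more days. The two ends of each dose-response curve, placebo and the top dose, have the longest window; the two lowest doses have the shortest. The five arms in a fit therefore cannot be expected to share one residual variance.

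SAP 7.5 leaves the error form open. Standard software would then apply one constant variance, which averages over quiet and noisy arms and gives standard errors too small where the data are noisiest. The exposure-response parameter estimates are a secondary endpoint (SAP 4.2), and SAP 7.5 uses both their intervals and AIC to choose the model, so the error form bears on interval width and possibly on model choice.

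**Working it through.** The documents give no AUEC SD, visit SD or interval to reproduce. The first two steps need only the schedule and an error structure. The coverage figures need further assumptions.

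**1. Trapezoid weights.** Inputs: lipid visits on Days 1, 2, 3, 4, 5, 7, 10, 14, 21, 28, 35, 42, 56, 70 and 84 (SAP Attachment A), cut at Day 42, 56 or 84. Baseline-adjusted AUEC = Σ wᵢ(Yᵢ − Y₀). The windows are 41, 55 and 83 days from dosing. The net weight on Y₀ is the window minus 0.5, so 40.5, 54.5 and 82.5 days.

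**2. SD from the window alone.** With independent visit errors of SD s, Var(AUEC) = s²[(Σwᵢ)² + Σwᵢ²].
- 42-day arms: 40.5² + 213.25 = 1853.5, SD = 43.1s
- 56-day arms: 54.5² + 360.25 = 3330.5, SD = 57.7s
- 84-day arms: 82.5² + 752.25 = 7558.5, SD = 86.9s

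The 84- to 42-day ratio is 2.02 and the 56- to 42-day ratio 1.34, whatever s is. With exponentially correlated errors (range 7 to 60 days) the 84- to 42-day ratio is 2.08-2.58. With baseline error removed it is 1.58-1.88.

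**3. Adding response variation.** With visit SD 12 mg/dL, assumed arm means and a between-subject response CV of 30-50%, placebo/low is 1.97-1.88 and high/low 2.42-2.94.

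**4. What a constant-variance fit does.** Take arm SDs 2 : 1 : 1 : 4/3 : 2 (placebo, low, intermediate low, intermediate high, high). The pooled SD is √[(4 + 1 + 1 + 1.78 + 4)/5] = 1.53. That is 77% of the true SD at placebo and high dose, and 153% at the two lowest doses.

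**5. Coverage of the fitted mean.** Assumptions: 8 per arm, SAP doses, ED50 at the intermediate high dose, maximum effect 12 times the 42-day SD, nominal 95% intervals; about 800 Emax or 4000 linear runs. Simulation error for 800 runs near 90% is √(0.9 × 0.1/800), about 1 point. Entries are % coverage, evolocumab / alirocumab.

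| Arm SDs | Fit | Placebo | Low | High |
|---|---|---|---|---|
| Equal | Emax | 95.1 / 94.2 | 93.2 / 95.5 | 95.2 / 95.5 |
| 2, 1, 1, 1.33, 2 | Emax | 84.4 / 87.1 | 98.9 / 97.7 | 89.1 / 85.8 |
| 2, 1, 1, 1.33, 2 | Linear | 94.0 / 94.1 | 95.1 / 95.5 | 88.1 / 88.4 |
| 1.7, 1, 1, 1.25, 1.7 | Emax | 87.5 / 89.4 | 97.4 / 97.6 | 91.2 / 89.1 |
| 1.5, 1, 1, 1.4, 2.5 | Emax | 96.6 / 94.8 | 99.0 / 98.5 | 80.0 / 80.9 |
| 1.2, 1, 1.05, 1.6, 3 | Emax | 99.0 / 98.4 | 99.2 / 99.2 | 75.3 / 78.1 |
| 2, 1, 1, 1.33, 2, weights 1/duration² | Emax | 94.0 / 94.7 | 95.6 / 94.5 | 95.9 / 95.5 |

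**6. Coverage of the model parameters.** Assumptions: evolocumab doses, drug area −3000·D/(D + 120) mg·day/dL, 30% response CV, visit SD 8 / 12 mg/dL. Arm SDs for placebo/21/35/70/140 mg are 699/376/404/578/854 and 1048/544/555/767/1156. There were 1500 trials per noise level; the 12% / 22% of fits with ED50 at a search limit were dropped.

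| Quantity | Constant variance | HC3 | Constant variance, equal arm SDs |
|---|---|---|---|
| 140 mg effect | 89 / 89 | 96 / 96 | 95-97 (companion run) |
| E0 | 94 / 93 | not run | not run |
| Emax | 87 / 86 | 91 / 91 | 91 / 90 |
| ED50 | 84 / 79 | 85 / 81 | 86 / 81 |

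Unequal variance costs Emax 91 − 87 = 4 and 90 − 86 = 4 points, and ED50 86 − 84 = 2 and 81 − 79 = 2 points. The rest of their shortfall is present with equal variances: it is curve nonlinearity, since the assumed ED50 of 120 mg lies close to the top dose of 140 mg. The sigmoidal and exposure models were not simulated.

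**The case against.** The strongest reply is that a reader might infer that the SAP prescribes one variance for all arms. It does not. It names a residual term and leaves its form open, so the defect is an omission, and the harm follows only if the default is used. That stands.

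A reader might also infer that intervals at both ends of the curve are always too narrow. The table does not support this. Placebo coverage is about 94% in the linear fit and 95-99% when high-dose spread dominates; it falls to 84-89% only in the Emax fits where window noise dominates.

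A third tempting reading is that planning of the future similarity study is compromised. The primary endpoint is the value and variability of the PD metrics at each dose, and SAP 7.3.1 reports SD and CV separately for each arm. Those figures do not pass through the pooled model. The modelling is exploratory in aim, with no test or decision threshold, and an interval for the 140 mg effect is not a named output.

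Finally, the fix does little for ED50 and only partly repairs Emax. That too stands. The objections limit the scope of the point, but they do not supply the missing variance specification. The high-dose shortfall appears in every unequal-variance scenario tried and disappears in the equal-variance control.

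**Conclusion.** The point holds for the AUEC dose- and exposure-response models, as an omission in SAP 7.5. The schedule and the single subtracted baseline make the AUEC SD about twice as large in the 84-day arms as in the 42-day arms, with a range of about 1.6 to 2.6 depending on the error structure assumed. Under constant variance, nominal 95% intervals at the high dose cover about 86-92% in most scenarios, and 75-81% if response spread at the top dose dominates. Emax intervals cover 86-92% when response spread is included, but part of that is nonlinearity.

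These coverage figures rest on assumed visit SDs, response CVs and curve shapes, none of which is in the documents. The 95% level is also assumed. The conclusion concerns interval width, not the mean curve, and does not extend to the ΔLDL-Cmin models, whose response is not a sum over time.

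**What to change.** Add a sentence to SAP 7.5: for the AUEC dose- and exposure-response models, standard errors and confidence intervals will come from an HC3 sandwich covariance or a bootstrap stratified by treatment arm, or the model will carry an arm- or duration-dependent residual variance. Report residual SD by arm beside each fit, and state the confidence level.

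HC3 brought the 140 mg interval to 94-97% in most runs (93-94% in one) and raised Emax coverage by 2-5 points. Weighting by duration squared restored 94-96% where the arm SDs followed the window length; by itself it does not allow for response spread that grows with dose. A common AUEC window would remove the window part, but it would change the primary endpoint and leave the dose-related part.

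The cost is one sentence and a standard software option, with no new data. Some intervals will become slightly wider. The nonlinearity affecting Emax and ED50 remains and should be acknowledged when those intervals are reported.

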5.2.1 Inclusion Criteria

Subjects who meet all of the following inclusion criteria will be eligible to participate in the study:

- 1. Subject signs an IRB approved written informed consent and privacy language as per national regulations (e.g., Health Insurance Portability and Accountability Act authorization) before any study related procedures are performed.
- 2. Subject is a healthy man or woman, 18 to 55 years of age, inclusive, who has a body mass index of 18.5 to 32.0 kg/m², inclusive, at Screening.
- 3. Subject has a LDL-C level >=100 and <=190 mg/dL inclusive, at Screening.

- 4. Subject has normal medical history findings, clinical laboratory results, vital sign measurements, 12 lead electrocardiogram (ECG) results, and physical examination findings at Screening or, if abnormal, the abnormality is not considered clinically significant (as determined and documented by the investigator or designee).
- 5. Subject must have a negative test result for alcohol and drugs of abuse at screening and Check-in (Day -1).
- 6. Female subjects must be of non-childbearing potential or, if they are of childbearing potential, they must: 1) have been strictly abstinent for 1 month before Check in (Day -1) and agree to remain strictly abstinent for the duration of the study and for at least 1 month after the last application of study drug; OR 2) be practicing 2 highly effective methods of birth control (as determined by the investigator or designee; one of the methods must be a barrier technique) from at least 1 month before Check in (Day -1) until at least 1 month after the last application of study drug.
- 7. Male subjects must agree to practice 1 highly effective method of birth control (as determined by the investigator or designee) from at least 1 month before Check in (Day-1) until at least 1 month after the last application of study drug.
- 8. Subject is highly likely (as determined by the investigator) to comply with the protocol defined procedures and to complete the study

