Attachment A. Pharmacokinetic, Pharmacodynamic, and Biomarker Sample Collection Schedule

Pharmacokinetic Sample Collection

Pharmacokinetic blood samples (5 mL) for determination of evolocumab or alirocumab concentration will be collected at the following time points:

- Day 1: 0 (pre-dose), 0.5, 1, 2, 3, 4, 6, 8, 12, 24 h
- Day 2, 3, 4, 5, 6, 7, 10, 14, 21, 28, 35, 42, 56, 70, 84

Blood samples will be collected by direct venipuncture or by inserting an IV catheter into the subject's forearm region. Each blood sample will be labeled with subject number, study number, study day, time point, event, and a barcode that matches that belonging to the subject.

Pharmacodynamic Sample Collection

Blood samples (5 mL) for primary pharmacodynamic biomarker (peripheral blood LDL-C) and secondary pharmacodynamic biomarker (peripheral blood ApoB) assessment will be collected at the following time points:

- Screening (Day -21 to -2)
- Day -1 (check-in)
- Day 1: 0 (Pre-dose) and 24 h (Day 2)
- Day 3, 4, 5, 7, 10, 14, 21, 28, 35, 42, 56, 70, 84

Blood samples will be collected by direct venipuncture or by inserting an IV catheter into the subject's forearm region. Each blood sample will be labeled with subject number, study number, study day, time point, event, and a barcode that matches that belonging to the subject.

Exploratory PD Biomarkers

Exploratory PD biomarkers will be evaluated using plasma proteomics and small RNA transcriptomics. Whole blood samples (5 mL) will be collected and processed for plasma at the following time points:

- Day -1 (check-in)
- Day 1: 0 (pre-dose), 0.5, 1, 2, 3, 4, 6, 8, and 12 h; 24 h (Day 2)
- Day 3, 4, 5, 6, 7, 7, 10, 14, 21, 28, 35, 42, 56, 70, 84

Blood samples will be collected by direct venipuncture or by inserting an IV catheter into the subject's forearm region. Each blood sample will be labeled with subject number, study number,

study day, time point, event, and a barcode that matches that belonging to the subject. All blood samples will be processed for preparation of plasma.

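### SAP 7.5 models absolute LDL-C change with no baseline covariate, which costs the Emax and ED50/EC50 fits some precision but does not bias them

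*SAP*

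**What the plan says.** SAP 7.5 models dose-response and exposure-response separately for each drug, pooling its four dose groups with placebo. The two responses are baseline-adjusted LDL-C AUEC and the maximum LDL-C decrease. Six equations are listed: linear, Emax and sigmoidal, each in dose and in AUC. None has a baseline term, and the section closes by saying that the models carry a residual error term but "will not include any random effects or covariate evaluation on fixed effect".

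SAP 6.1 fixes the baseline: "For baseline adjusted measures, samples from Day 1, time 0 will be used for calculating this derived metric", with Day -1 and then Screening as fallbacks. SAP Attachment A confirms that a Day 1 pre-dose lipid sample is taken. Protocol 5.2.1 sets the entry range: "Subject has a LDL-C level >=100 and <=190 mg/dL inclusive, at Screening".

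SAP 7.3.1 allows AUEC normalised to baseline (pAUEC) as an optional derived measure. SAP 7.5 does not name it as a response. SAP 4.2 lists the exposure-response parameter estimates as a secondary endpoint.

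**The concern.** Subtracting baseline does not remove all of its influence. Two sources of noise remain.

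- **Starting level.** If the drug lowers LDL-C by a given percentage, the absolute fall is larger in someone who starts higher. Chance differences in baseline between groups of 8 then move the points through which the curve is drawn.
- **Day 1 error.** The baseline is one reading. Its error enters every response with opposite sign, and the observed baseline partly predicts it.

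A baseline covariate addresses both in part, and the data are already collected. At stake is the precision of Emax and ED50/EC50, which bear on the sensitive dose range that Protocol 5.8.2 sets out to find. The residual SD that could inform later similarity studies is affected too. SAP 7.5 also uses parameter uncertainty to choose between models. The per-arm summaries of the primary endpoints are not affected.

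**Working it through.** **Plan's figures.** 9 arms x 8 = 72, and 72 + 14 replacements = 86, as SAP 3.2 states. Each drug model has 5 groups x 8 = 40 planned subjects. The Emax model has 3 parameters, leaving 40 - 3 = 37 residual df, or 36 with a baseline term. SAP 3.2 reports no power calculation, and no SD is given anywhere, so every figure below rests on assumptions.

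**Starting level.** Assume baselines uniform on 100-190 mg/dL.
- SD = (190 - 100)/√12 = 26.0 mg/dL.
- SE of one arm's mean baseline = 26.0/√8 = 9.2; SE of the difference between two arms = 9.2 x √2 = 13.0.
- Under a proportional fall, the fall at 190 is 190/100 = 1.9 times that at 100. At a 50% fall, a 13.0 mg/dL difference in arm-mean baselines shifts the difference in falls by 0.5 x 13.0 = 6.5 mg/dL.

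**Day 1 error.** Write the observed baseline as B + e. The response contains -e, and the share of the variance of e predictable from B + e is σe²/(σB² + σe²). With assumed σB = 25:
- σe = 8: 64/(625 + 64) = 9%.
- σe = 13: 169/(625 + 169) = 21%.

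Selection at Screening narrows the spread of B and so raises these shares.

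**Simulated trials.** Each set compares the SAP's Emax model with the same model plus one additive baseline term, at 8 subjects per group.
- **Set 1:** 500 runs per setting; evolocumab doses 0/21/35/70/140 mg; maximum decrease; baseline uniform on 100-190 or normal (135, SD 20) clipped to that range; drug effect 50% or 60% of baseline; placebo decrease 10%; residual SD 8 or 12 percentage points; ED50 30 or 60 mg; no separate Day 1 error among the assumptions.
- **Set 2:** 600 runs; within-subject SD 8-13 mg/dL; true baseline about N(125, SD 25), kept if Screening is 100-190; maximum fall 60%; variation in response 20-35%; ED50 0.25 or 0.5 of the high dose; same window in all arms.
- **Set 3:** 300 runs; maximum decrease; similar to set 2, with one post-dose reading for the nadir.
- **Set 4:** 250 runs; ED50 0.25 of the high dose; Day 1 error included.
- **Set 5:** 200 runs; all 14 post-dose readings; Day 1 error included; maximum decrease and AUEC; common windows and 42/56/84-day windows.

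Reduction from the additive term:

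| Set | Residual variance, fall proportional | Residual variance, fall independent of baseline | Spread of log ED50 | SE (or spread) of fitted high-dose response |
|---|---|---|---|---|
| 1 | 10-40% | 0% | proportional 2-20%; independent: 0.45 to 0.47 (slightly worse) | not computed |
| 2 | 19-46% | not run | proportional 14-27% | proportional 8-22% |
| 3 | 15-31% | 3-14% | proportional 0-20%; independent about neutral | proportional 7-19% |
| 4 | 8-27% | 0-9% | proportional 8-16%; independent: ratio 0.84-1.09 | not computed |
| 5 | 19-34% | 2-24% | usually, not always, smaller | proportional 9-17%; independent 0-6% |

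In set 1, residual SD is converted to variance. The smallest gain is 17.4 to 16.5, so 1 - (16.5/17.4)² = 10%. The largest is 16.1 to 12.5, so 1 - (12.5/16.1)² = 40%. The log ED50 extremes are 0.82 to 0.80 (2%) and 0.61 to 0.49 (20%).

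**Scaling instead of adding.** Set 1 also fitted a model with E0 and Emax scaled by baseline. Under a proportional fall it lowered residual SD by 6-27%, against 5-22% for the additive term. When the fall did not depend on baseline, scaling did harm: residual SD rose from 13.4 to 16.0, while the additive term left it at 13.4.

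**Bias.** Median Emax and ED50 were essentially the same with and without baseline in set 1, as was median ED50 in set 2.

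**The case against.** The strongest case for leaving SAP 7.5 alone has five parts.

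- **Parsimony.** With 40 subjects and up to four parameters (sigmoidal), a model without covariates is defensible in a pilot whose secondary objective is to explore PK/PD relationships. No error rate, sample size or primary endpoint depends on it. This stands, and it limits the importance of the point. It is not a strong reason to omit a term that costs 1 of about 37 df.
- **Wrong shape.** A proportional effect has a steep baseline slope at high dose and a shallow one on placebo, so a single additive slope is a compromise. This stands.
- **AUEC windows.** Follow-up is 42, 56 or 84 days by arm, so Day 1 error enters AUEC multiplied by a window that differs up to twofold (84/42 = 2). One slope cannot match that exactly. This stands, but set 5 used those windows and residual variance still fell.
- **No documented effect size.** If the fall does not depend on baseline, the gain can be nil. This stands, and the stated range therefore starts at zero.
- **pAUEC.** SAP 7.3.1 already permits a baseline-normalised measure. It is optional, and SAP 7.5 does not model it, so the answer is only partial.

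A narrow reading of the closing sentence would bar only a covariate search. The six equations still contain no baseline term, so that reading changes nothing.

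**Conclusion.** The point holds as a loss of precision in a secondary analysis. In most settings, one centred baseline term lowers residual variance by roughly 15-45% if the fall is proportional to baseline (extremes 8% and 46%) and by about 0-25% if it is not. The gain in ED50 precision is smaller and not consistent. All of this rests on assumed SDs, effect sizes and response shapes.

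A reader might infer more than the documents support:

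- That the fits ignore the Day 1 baseline. They do not: both responses are changes from it. What is missing is baseline as a covariate or as a scaling.
- That baselines span 100-190 mg/dL on Day 1. That range applies at Screening; Day 1 values may fall outside it, and their spread is not given.
- That Emax or ED50/EC50 is biased. The simulations show no material shift.
- That an additive term removes the whole effect of starting level. It removes part of a proportional effect.
- That the gain is worth 1.2 to 1.8 times as many subjects. That follows only from the proportional-fall, common-window cases.

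**What to change.** In SAP 7.5, replace the no-covariate sentence with a pre-specified term: each dose- and exposure-response model includes centred Day 1 LDL-C as its only covariate, with no covariate search. For the Emax form:

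Response = E0 + Emax·x/(x + ED50) + β·(baseline - mean baseline),

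where x is dose, or AUC with EC50 in place of ED50. Report residual SD and parameter estimates with and without the term.

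As a sensitivity analysis, also fit a baseline-normalised response: percent change for maximum decrease and pAUEC for AUEC. It should stay a sensitivity analysis, because scaling loses precision if the fall does not depend on baseline. It does not remove the unequal follow-up windows either.

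Cost: one extra parameter per model (about 1 of 37 df), slightly more reporting and no new data. If response does not depend on baseline, there may be little or no gain.
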